8.4 Overdose

For this study, any dose of RXC004 greater than the daily assigned dose will be considered an overdose.

Investigators should be advised that any patient who receives an overdose should be monitored closely, managed with appropriate supportive care and followed up expectantly. There are no data regarding RXC004 overdose in humans. An overdose and AEs should be treated per standard medical practice.

Dosing details should be captured in the eCRF. If the patient receives a dose of a study drug that exceeds protocol specifications and the patient is symptomatic, then the symptom(s) should be documented as AEs in the eCRF and, if serious, submitted to the Sponsor’s

designated safety contact on an SAE Report Form. Do not record the overdose as an AE if the patient is not symptomatic.

For this study (Module 3), an overdose of pembrolizumab will be defined as any dose of 1000 mg or greater.

No specific information is available on the treatment of overdose of pembrolizumab. In the event of overdose, the participant should be observed closely for signs of toxicity. Appropriate supportive treatment should be provided if clinically indicated.

8.5 Human Biological Samples

Instructions for the collection and handling of biological samples will be provided in the study specific laboratory manual. Samples should be stored in a secure storage space with adequate measures to protect confidentiality. For further details on Handling of Human Biological Sample see Appendix C.

Samples will be stored for a maximum of 15 years from the date of the issue of the CSR in line with consent and local requirements, after which they will be destroyed/repatriated.

- Pharmacokinetic (PK) samples will be disposed of after the Bioanalytical Report finalisation or six months after issuance of the draft Bioanalytical Report (whichever is earlier), unless consented for future analyses.
- Pharmacokinetic samples may be disposed of or anonymised by pooling. Additional analyses may be conducted on the anonymised, pooled pharmacokinetic samples to further evaluate and validate the analytical method. Any results from such analyses may be reported separately from the Clinical Study Report (CSR).

8.5.1 Pharmacokinetics

Venous blood samples (2 mL) for determination of concentrations of RXC004 in plasma, this may also permit investigation of any significant metabolites. Samples will be taken after a single dose of RXC004 in Cycle 0 Day 1 at designated times (Table 15, Table 16, and Table 18) up to 48 h post-dose and again at Cycle 1 Day 15 at designated times up to 24 h post-dose. Cycle 0 may be 3-7 days in duration to allow for flexibility in scheduling the full PK time course at Cycle 1 Day 15 to avoid weekend sampling if required. CCI

CCI if required. The date and time that the last dose of RXC004 was administered prior to Cycle 1 Day 15 and the date and time of collection of each sample will be recorded.

The timing of the PK samples may be adjusted during the study, dependent on emerging data, in order to ensure appropriate characterisation of the plasma concentration-time profiles. The total number of samples and the total volume of blood taken from each patient will not exceed that outlined in the Lab Manual.

If a patient misses any doses of RXC004 within 3 days of PK sampling, please contact the Sponsor representative as to any effect on the changes required on the timing of the PK assessments. All other assessments, including laboratory safety assessments, vital signs and RECIST should continue to be performed as per study plan, relative to baseline assessments.

Samples will be collected, labelled, stored and shipped as detailed in the Laboratory Manual.

8.5.1.1 Determination of Drug Concentration

Samples for determination of RXC004 concentrations in plasma will be analysed using an appropriate bioanalytical method. Full details of the analytical method used will be described in a separate bioanalytical report.

All samples still within the known stability of the analytes of interest at the time of receipt by the bioanalytical laboratory will be analysed.

In addition, the pharmacokinetic samples may be subjected to further analyses in order to investigate the presence and/or identity of drug metabolites. Any results from such analyses will be reported separately from the Clinical Study Report.

Incurred sample reproducibility analysis, if any, will be performed alongside the bioanalysis of the test samples. The results from the evaluation, if performed, will be reported in a separate Bioanalytical Report.

PK parameters will be estimated for each patient using WinNonlin® (Phoenix 64 V8 or higher) or suitable alternative. The following parameters will be derived, where appropriate, from the individual plasma-concentration-versus-time profiles of RXC004.

Where appropriate the following RXC004 plasma pharmacokinetic parameters will be estimated. These include:

Single dose:	
• C_{max}	Maximum observed plasma concentration
• t_{max}	Time to C _{max}
• C_{min}	Minimum observed concentration across the dosing interval
• λz	Terminal rate constant
• t^{1/2}	Terminal half-life
• AUC₀₋₂₄	Area under the plasma concentration-time curve from zero to 24 hours
• AUC_{0-t}	Area under the plasma concentration-time curve from zero to the time of the last quantifiable concentration
• AUC_{0-∞}	Area under the plasma concentration-time curve from zero to infinity
• AUC_τ	Area under the plasma concentration-time curve across the dosing interval
• CL/F	Total plasma clearance after oral administration
• Vz/F	Apparent volume of distribution after oral administration

• MRT	Mean residence time
• R_{ac}	Accumulation ratio based on AUC _τ and C _{min} after the first and the last dose
• Swing	(C _{max} -C _{min})/C _{min}

Dose proportionality of exposure parameters will be explored. In addition to dose normalisation of Cmax and AUC values.

Additional PK parameters may be calculated as appropriate.

8.5.2 Pharmacodynamics

8.5.2.1 Collection of Samples

CCI

CCI

CCI

CCI

CCI

CCI

8.6 Human Biological Sample Biomarkers

8.6.1 Collection of Mandatory Samples for Biomarker Analysis

By consenting to participate in the study the patient consents to participate in the mandatory research components of the study.

Samples for biomarker research are required and will be collected from all participants in this study as specified in the SoA. CCI

CCI

CCI

Details for collection, volumes, storage, and shipment of biologic samples will be detailed in a separate Laboratory Manual.

8.6.1.1 CCI

Module 1 Centralised Pre-Screening in the UK

CCI from UK patients will be sent to CCI

CCI, during the centralised pre-screening phase in Module 1. This analysis is required to investigate the presence of RNF43 mutants required to be eligible for Module 1 of the study (see

Appendix F). Analysis will occur before enrolment, and data will be shared with investigators and patients, to aid future treatment decisions.

CCI [REDACTED] will also be screened from the CCI [REDACTED] These data will be used to retrospectively investigate whether CCI [REDACTED]
CCI [REDACTED]

CCI [REDACTED] performed by CCI [REDACTED]
CCI [REDACTED]
CCI [REDACTED]

Module 1 Local Testing - UK

PDAC patients with prior documented RNF43 LoF mutations (per Appendix F) will also be eligible for Module 1 of the study provided that the panel used is fully CCI [REDACTED]
CCI [REDACTED]
CCI [REDACTED] If patients are enrolled in the study based on local laboratory assessments, then an optional archival CCI [REDACTED]
CCI [REDACTED] will be collected at screening and sent for central genetic screening as described in Section 5.8. If an archival CCI [REDACTED] is not available or not consented to, then a sample of the study baseline CCI [REDACTED] may be sent for the central genetic screening.

Module 1 Centralised Pre-Screening in Australia

In Australia, patients with eligible RNF43 LoF mutations detected in archival FFPE tumour samples (see Appendix F) will be identified via their participation in the MoST Framework Protocol screening programme (Australia New Zealand Clinical Trials Registry:

ACTRN12616000908437). CCI [REDACTED]

CCI [REDACTED] If an CCI [REDACTED]
CCI [REDACTED] is not available or not consented to, then a sample of the study CCI [REDACTED] CCI [REDACTED]
CCI [REDACTED] may be used for this purpose.

Module 2 and Module 3 Genetic Analysis

An CCI [REDACTED] (mandatory, if available) will be collected at screening from patients enrolled in Module 2 and Module 3, for CCI [REDACTED] if there is a CCI [REDACTED] of CCI [REDACTED] that may CCI [REDACTED] This research will involve analysis of CCI [REDACTED]

8.6.1.2 Exploratory Biomarkers

CCI [REDACTED]

The study mandates that CCI [REDACTED] are collected at baseline and 'on treatment' at time points specified in the SoA, as long as it is technically feasible and safe to do so. CCI [REDACTED]

CCI [REDACTED] that may be assessed include (but are not limited to), CCI [REDACTED]

CCI [REDACTED]

CCI [REDACTED]. The CCI [REDACTED] of these CCI [REDACTED] may be correlated to clinical response.

CCI [REDACTED]

CCI [REDACTED] may be prepared from whole blood samples obtained from patients at timepoints specified in the SoA. Quantification of CCI [REDACTED] and/or CCI [REDACTED]

CCI [REDACTED] Analysis may include (but is not limited to), the CCI [REDACTED] of CCI [REDACTED]

Correlations with outcome data may be performed on CCI [REDACTED] with the aim of identifying useful CCI [REDACTED] thresholds for identifying patients likely to receive benefit.

CCI [REDACTED]

Blood samples for analysis of CCI [REDACTED] will be obtained from all patients as specified in the SoA. Overall CCI [REDACTED] and/or CCI [REDACTED] in CCI [REDACTED] may be assessed using CCI [REDACTED] Such measurements may be correlated with response.

CCI [REDACTED]

Blood sample for analysis of CCI [REDACTED] will be obtained from patients at timepoints specified in the SoA. The concentrations of a panel of relevant CCI [REDACTED], CCI [REDACTED] CCI [REDACTED]. Such measurements may be correlated with response.

CCI [REDACTED]

CCI [REDACTED] will be taken from a subset of patients recruited by sites within close proximity to Redx Pharma. CCI [REDACTED] CCI [REDACTED] will be used for analysis of CCI [REDACTED] using CCI [REDACTED] Such measurements may be correlated with response.

CCI [REDACTED]

CCI [REDACTED] frequently increased in CCI [REDACTED]. Blood samples for CCI [REDACTED] will be obtained from patients at timepoints specified in the SoA and analysed locally. CCI [REDACTED] may be correlated with response.

8.7 Health Economics

Not applicable in this study

9 STATISTICAL CONSIDERATIONS

The module specific statistical considerations can be found in Section 10.9 (PDAC) and Section 11.9 (BTC - monotherapy) and Section 12.11 (BTC – combination therapy).

9.1 Statistical Hypotheses

The statistical hypotheses for testing the activity of RXC004 in Module 1 (pancreatic cancer), and Modules 2 and 3 (biliary tract cancer) independently are:

$$H_0 : p \leq p_0$$

$$H_1 : p \geq p_1$$

Where H_0 is the null hypothesis, p is the observed response rate, p_0 is the response rate for available treatment options – CCI, H_1 is the alternative hypothesis and p_1 is the target response rate – CCI.

The primary summary measure for Module 1 and Module 2 is the progression free survival rate at 6 months. For module 1 the corresponding p_0 and p_1 are CCI% and CCI%. For Module 2 the corresponding p_0 and p_1 are CCI% and CCI%. The primary summary measure for Module 3 is the objective response rate. For Module 3 the corresponding p_0 and p_1 are CCI% and CCI%.

9.2 Sample Size Determination

The sample size determination for each module can be found in the module-specific statistical considerations - Section 10.9.1 for Module 1 (PDAC), Section 11.9.1 for Module 2 (BTC - monotherapy), and Section 12.11.1 for Module 3 (BTC – combination therapy).

9.3 Populations for Analyses

The following populations are defined:

Table 14 **Populations for Analysis**

Population/Analysis set	Description
Full analysis set / Safety	All patients who enrolled and received at least one dose of RXC004 in Modules 1 and 2, and at least one dose of RXC004 or pembrolizumab in Module 3.
CCI	CCI CCI CCI

Population/Analysis set	Description
	CC1 CC1 CC1 CC1
PK analysis set	All patients in the safety analysis set who have had at least one blood sample.

9.4 Statistical Analyses

The statistical analysis plan will be finalised prior to DBL and it will include a more technical and detailed description of the statistical analyses described in this section. This section is a summary of the planned statistical analyses of the most important endpoints including primary and key secondary endpoints.

9.4.1 General Considerations

The study data is planned to be analysed and reported based on all patient data at the primary completion data cut-off date (approximately 24 weeks after Cycle 1 Day 1 for the last patient in Modules 1 and 2, or 90 days after the last dose of pembrolizumab for the last subject in Module 3), or at the End of Study, whichever comes first. Depending on recruitment the data may be reported separately for each module. If reported together in one CSR the efficacy data will be presented separately for each module and not pooled. Baseline characteristics and safety data will be presented separately and selected data may be pooled, which will be detailed in the SAP.

All analyses, summaries and listings will be performed using SAS software (version 9.3 or higher). For categorical variables the frequency and percentage will be presented. For continuous variables, the sample size (n), mean, median, and standard deviation, as well as the minimum and maximum values will be presented. Missing data will not be imputed unless otherwise stated.

A baseline assessment will be defined as the last assessment performed prior to the first dose of study treatment. While many of these assessments will be performed on the day of the first dose, others will be performed during screening. If a patient is missing an assessment typically performed on the day of the first dose, screening values may be substituted as baseline.

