9.4.2 Efficacy

9.4.2.1 Primary Endpoint(s)

Modules 1 and 2:

The primary endpoint is the progression free survival rate at 6 months, based on investigator

RECIST 1.1 assessments.

Progression free survival rate at 6 months is defined as the proportion of patients who remain alive and free of progression at 6 months.

Module 3:

ORR, defined as the proportion of patients with a best overall response of CR or PR, based on local investigator assessment, as defined in RECIST 1.1.

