9.4.2.2 Secondary Endpoint(s)

Objective response rate is defined as the proportion of patients with a best overall response of CR or PR, based on local investigator assessment, as defined in RECIST 1.1. Confirmation of response is required for declaring PR or CR as the BOR. A confirmed response is defined as a CR or PR followed by a CR or PR a least 4 weeks later. The ORR will be summarised with accompanying 90% confidence interval calculated using the Clopper Pearson method. This will be calculated on the full analysis set and the evaluable analysis set. In the summary tables the incidence of unconfirmed responses will be presented as well as the patients with confirmed responses.

Disease control rate (DCR) is defined as the proportion of patients with a best overall response of either CR, PR or stable disease (SD) for at least 6 weeks (corresponding to SD for at least 1 scheduled scan post baseline). A time window of 1 week around the visit will be applied. The DCR and associated 90% confidence interval, calculated using the Clopper Pearson method will be presented. This will be calculated on the full analysis set and the evaluable analysis set.

Progression free survival is defined as the time from first dose of study treatment until the date of disease progression or death (by any cause in the absence of progression), regardless whether the patient withdraws from the assigned study treatment or receives another anticancer prior to progression. Patients who have not progressed or died at the time of analysis will be censored at the time of the latest date of RECIST v1.1 assessment of their last evaluable scan; however, if the patient progresses or dies after 2 or more missed scheduled scanning visits, the patient will be censored at the time of their last evaluable scan prior to the missing scan visits. If the patient has no evaluable visits or does not have baseline data they will be censored at 0 days unless they die due to progression within 2 scan visits of baseline. Progression free survival will be listed by patient and will be presented graphically using Kaplan-Meier plots. Median PFS, together with 3 month, 6 month and 12 months PFS rates will be estimated. The estimate for PFS rate at 6 months is the primary endpoint as detailed in Section 9.4.2.1.

[figure not shown]

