10.9.1 Module 1 Sample Size Determination

The method by Frewer et al (Frewer et al 2016), together with the totality of the data collected, will be used to guide go/no-go decision making:

For the population under investigation, the standard of care of liposomal irinotecan in combination with 5-FU/Leucovorin showed a 6-month PFS rate of **CCI**% (NAPOLI-1 trial, Wang-Gillam et al 2016), which will be the **CCI** in our study. An improvement to **CCI**% in 6-month PFS would be considered clinically significant in this patient population (**CCI**). Statistically, the hypothesis that will be tested is $H_0: p < \text{CCI}$ versus $H_1: p > \text{CCI}$, where p is the proportion of patients who live 6 or more months without disease progression. **CCI**

CCI
CCI
CCI If **CCI**

patients or fewer are progression free at 6 months RXC004 would be determined not worthy of further investigation with this patient population. The type I and II error rates associated with this testing are 0.06 and 0.10, respectively. The PFS at 6 months estimates will be used to guide the decision for onward development. The totality of the data, including the results from the secondary endpoints will be used to in the final decision.

Approximately **CCI** patients are expected to be enrolled in order for **CCI** patients to be evaluable.

Note: “Enrolled” means the subject has completed the main study CRF and has been assigned to a treatment arm.

MODULE 2 (BTC)

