### 4.11.2 Primary Efficacy Variable(s)

Primary efficacy analyses will be conducted on the FAS. A listing containing information on target, non-target lesions, new lesions, overall response will be provided (ordered by patient and visit).

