#### 4.11.2.1 Progression Free Survival

PFS is defined in Section 3.2.1.1.

Kaplan-Meier analyses will be conducted for each module. Survival plots will be produced to present Kaplan-Meier estimated curves. In addition, the following parameters estimated from the Kaplan-Meier curves will be provided for each group:

- Median PFS and corresponding 95% CIs
- PFS rate at 3, 6 and 12 months and corresponding 90% CIs and 95% CI (one month = 30.4375 days).

PFS will be listed for all patients in the FAS.

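### Modules 1 and 2: the go/no-go hurdle and its error rates belong to a count of patients at 6 months, the visible primary analysis is a Kaplan-Meier rate, and the data cut and one censoring rule do not fit the defined endpoint

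*Protocol*

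**What the plan says.** **Endpoint.** Protocol 9.4.2.1 gives the 6-month PFS rate as "defined as the proportion of patients who remain alive and free of progression at 6 months". SAP 3.2.1.1 agrees.

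**Decision rule.** In Protocol 10.9.1 (Module 1), if a redacted number of "patients or fewer are progression free at 6 months RXC004 would be determined not worthy of further investigation with this patient population". It adds: "The type I and II error rates associated with this testing are 0.06 and 0.10, respectively". Protocol 11.9.1 (Module 2) has the same kind of rule, with 0.06 and 0.20, and SAP 4.15 repeats both. A redacted number of "patients are expected to be enrolled in order for" a second redacted number to be evaluable. The hurdle guides the decision together with the totality of the data. Protocol 4.4.1.6 also refers to it for opening Cohort 2 of Module 2, unless the safety monitoring committee considers that tolerability compromised efficacy.

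**Analysis.** SAP 4.11.2: "Primary efficacy analyses will be conducted on the FAS". SAP 4.11.2.1 specifies Kaplan-Meier analyses only, giving the "PFS rate at 3, 6 and 12 months and corresponding 90% CIs and 95% CI (one month = 30.4375 days"). Protocol 9.4.2.2, after describing the Kaplan-Meier presentation of PFS, says: "The estimate for PFS rate at 6 months is the primary endpoint as detailed in Section 9.4.2.1".

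**Cut.** Protocol 9.4.1 sets it at "approximately 24 weeks after Cycle 1 Day 1 for the last patient in Modules 1 and 2"; SAP 4.2.4 is similar. PFS starts at C0D1 (SAP 3.2.1.1), and Cycle 0 lasts 3-7 days (Protocol 8.5.1).

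**Censoring.** Under SAP 3.2.1.1, a progression or death 12 + 1 weeks or more after the last scan is censored at that scan. A patient with no evaluable visit is censored at day 0 unless death occurs within 12 + 1 weeks of first dose. Protocol 9.4.2.2 limits that exemption to deaths due to progression.

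**The concern.** The stated error rates describe an integer count compared with an integer cut-off. The analysis returns a Kaplan-Meier percentage. No unredacted text gives the count's denominator, says how a patient of unknown 6-month status is scored, or says how the percentage meets the cut-off. ORR and DCR, by contrast, each get a Clopper-Pearson 90% interval on named sets (SAP 4.11.3).

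The cut and the censoring rules add a separate difficulty. Followed as written, they leave the last-enrolled patients short of the landmark. They also treat as censored some patients who, under the endpoint's own definition, have failed. The hurdle steers go/no-go in two modules, and a reader would take 0.06 as the false-go risk of the reported 6-month rate.

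**Working it through.** **Stated errors.** These cannot be reproduced, because n, p0, p1 and the cut-off are redacted. Many exact binomial rules round to 0.06/0.10 or 0.06/0.20. One assumed example is n = 24, p0 = 15%, p1 = 40%, go if 7 or more are progression free: type I error 0.057, power 0.904. The stated errors are therefore consistent with a count rule.

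**Cut.**
- Landmark: 6 × 30.4375 = 182.625 days.
- Cut for the last patient, from C0D1: 168 + (3 to 7) = 171-175 days.
- Shortfall: 7.625 to 11.625 days.
- Share of patients with under 6 months of follow-up at the cut, assuming even accrual:
  - over 12 months, 7.625/365 to 11.625/365 = 2.1-3.2%;
  - over 3 months, 7.625/91 to 11.625/91 = 8.4-12.8%.
- Any of these patients still event free cannot be classified at 6 months.
- The first scheduled scan after 6 months is Week 30: 210 ± 7 = days 203-217, beyond the cut for the last patients.

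**Known deaths, by the SAP rule.**
- Last scan at Week 6 (day 42), death at Week 20 (day 140): 140 − 42 = 98 days, which is at least 91. The patient is censored at day 42.
- Never scanned, death after day 91 and before day 182.6: the patient is censored at day 0.
- Both patients are failures under the endpoint definition.

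**Size, by simulation.** Assumptions: exponential PFS with a true 6-month rate of 25%, scans every 6 weeks ± 7 days, progression dated at the scan, the 91-day rule, and a median of 90 days from progression to death. The Kaplan-Meier estimate exceeds 25% even with complete scans, because a progression after the Week 24 scan is not seen until Week 30. The estimate is in effect the Week 24 rate: 0.25^(168/182.625) = 27.9%.

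| Patients who deteriorate with no further scan (assumed) | Kaplan-Meier, SAP rule | Kaplan-Meier, known deaths as events | Due to the rule (before rounding) |
|---|---|---|---|
| 0% | 27.7% | 27.7% | 0 |
| 10% | 29.5% | 29.1% | 0.4 points |
| 20% | 31.4% | 30.5% | 0.9 points |
| 30% | 33.5% | 31.9% | 1.5 points |

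At 20% unscanned the whole rise is 31.4 − 27.7 = 3.7 points. The rule accounts for 0.9; the rest is progression that was never documented, a missing-data problem.

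With complete scans and the cut at day 173, Kaplan-Meier is 27.3% (12-month accrual) or 25.6% (3-month accrual). With the cut at day 217 it is 27.8%. The cut therefore costs 0.5 or 2.2 points.

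**Estimator alone.** With complete scans, Kaplan-Meier gives 27.7% and the count 27.9%.

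**The case against.** The strongest reply is that the missing link may be behind the redactions. The evaluable-set definition and the text beside each hurdle are blacked out, and a denominator or a rule for unknown status could sit there. That stands, so the point cannot be that the plan lacks such a rule.

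Much of the rest of the reply also stands. With complete scans the estimators nearly agree. The cut is stated as approximate, and its effect is downward. Three-month accrual is an assumption, and hard to credit for a mutation found in 5-10% of pancreatic cancers. The unscanned share has no basis in the documents, and scans are planned until RECIST progression, including after treatment stops. The hurdle only guides a decision made on all the data.

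A reader might go further and infer that the true errors differ from those stated, because the count was sized on evaluable patients and the analysis uses the FAS. SAP 4.4.1 and 4.5 show that the two sets can differ, but not by how much, nor that the hurdle would be carried across unchanged. Nor does Kaplan-Meier by itself inflate the false-go risk. In four assumed designs with complete scans it was 0.054-0.057, against 0.057-0.059 for the exact count.

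The reply does not remove the stated rules themselves. The cut falls before the landmark, and known deaths before 6 months are censored.

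**Conclusion.** The point holds in a limited form. The hurdle and its errors belong to a count, the visible primary analysis is a Kaplan-Meier rate, and the documents do not show that the stated errors apply to that rate. They do not show that the errors are wrong either.

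Two visible rules conflict with the endpoint as defined. The cut is 8-12 days short for the last patient, which lowers the Kaplan-Meier rate by about 0.5 points (assumed 12-month accrual) or 2 points (assumed 3-month accrual). Censoring of known deaths raises it by about 0.4-1.5 points, given an assumed 10-30% unscanned and a true rate of 25%. These are modest effects in opposite directions. The day-0 exemption also differs between protocol and SAP.

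The case for acting is that the repair is specific and cheap. It also settles the comparison before results are seen in an open-label, single-arm study.

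**What to change.** 1. Report the binary 6-month endpoint already defined, on the analysis set for which the hurdle was set. Count every known progression or death before the landmark as a failure, give a Clopper-Pearson 90% CI, and compare the hurdle with that result. Keep Kaplan-Meier as supportive. Show patients of unknown status in a sensitivity analysis; scoring them all as failures is a convention, not a correction.
2. Align cut and landmark in one of two ways.
   - Keep 6 months, and move the cut so that the last patient has at least 6 months from C0D1 plus the next scheduled scan.
   - Define the landmark as the Week 24 scan, and restate the benchmark at that time. On an exponential curve a 25% 6-month rate becomes 27.9%.
3. Reconcile the day-0 exemption between Protocol 9.4.2.2 (death due to progression) and SAP 3.2.1.1 (any death).

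**Cost.** A short protocol and SAP amendment and one extra table. With the Week 24 landmark (window closes day 175) the cut moves 175 − (171 to 175) = 0-4 days later. With 6 months plus the Week 30 scan (window closes day 217) it moves up to 217 − (171 to 175) = 42-46 days later. The reported rate may be slightly less favourable. In the sensitivity analysis, if 5-10% of progression-free patients had no scan at Week 24 or later and were scored as failures, 27.9% would become 27.9 × 0.95 = 26.5% to 27.9 × 0.90 = 25.1%.
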